## 2.8.2 Statistical hypothesis, model, and method of analysis

Similar to the primary analysis, the secondary analysis will be interpreted in a purely descriptive manner due to the reduced sample size although hypothesis testing will still be performed for the specific secondary objectives.

For the continuous secondary endpoints BCVA change from baseline, CSRT change from baseline, and FCP thickness change from baseline, summary statistics will be produced for the baseline values, absolute values and the change from baseline values to month 12. The summary statistics for the baseline values, absolute values and the change from baseline values to month 12 will also be produced using the unadjusted CSRT and FCP thickness values. The course over time for the absolute values and for changes from baseline will be presented graphically for the treatment arms for CSRT and FCP thickness variables, showing the mean and SD per visit.

Tests comparing the changes in BCVA, CSRT and FCP thickness will be based on ANCOVA models, containing the baseline values of the dependent variables as continuous covariates, and center and treatment as categorical covariates. The LS ("adjusted") means for each treatment arm and estimates of the difference (DI - PRN) will be given along with the respective two-sided, 95% CI. Two-sided p-values will be presented for the treatment difference.

Additional sensitivity analyses of changes in BCVA and CSRT will be performed using all data from baseline to EoS. These sensitivity analyses will include descriptive analyses and a repeat of the ANCOVA outlined in the previous paragraph.

The total number of injections will be summarized as described in [Section 2.5.1.1](#). Additionally, the total number of visits and total number of TFIs (see [Section 2.1.1](#) for definition of TFI) to month 12 will be summarized for the two treatment arms descriptively. Note: All data up to EoS will be used for FAS.

Change in DRS from baseline to month 12 (improvement of 0, 1, 2, and  $> 2$  steps, or loss of 1, 2,  $> 2$  steps) will be summarized by presenting the number and percentage of patients in each treatment arm achieving the endpoint for FAS (LOCF). This improvement/ loss will only be derived for those patients with a DRS score of 1, 2, 3, or 4 at baseline and at month 12. In addition, a shift table will be produced to summarize the shift from baseline to month 12 in DRS score for FAS (LOCF).

Additional ANCOVA models for the primary outcome (visit-averaged change from baseline in BCVA from month 1 to EoT) will be performed with the following extra binary covariates (Yes, No):

- relevant changes of HbA1c (defined as any change of HbA1c (%) from baseline of  $> 1\%$ )
- relevant changes of systolic blood pressure (defined as any change of systolic blood pressure (mmHg) from baseline  $> 30$ )
- relevant changes of diastolic blood pressure (defined as any change of diastolic blood pressure (mmHg) from baseline  $> 20$ )
- relevant changes of cholesterol (defined as any change in cholesterol from baseline of (1) for female:  $\leq 2.38$  mmol/l; 92 mg/dl or  $\geq 6.06$  mmol/l; 234 mg/dl, (2) for male:  $\leq 2.12$  mmol/l; 82 mg/dl or  $\geq 4.97$  mmol/l; 192 mg/dl)
- relevant changes of HDL-cholesterol (defined as any change in HDL-cholesterol from baseline of  $\leq 1.04$  mmol/l; 40 mg/dl)
- relevant changes of LDL-cholesterol (defined as any change in LDL-cholesterol from baseline of  $\geq 3.38$  mmol/l; 130 mg/dl)
- relevant changes of triglycerides (defined as any change in triglycerides from baseline of  $\geq 1.71$  mmol/l; 150 mg/dl)

For each ANCOVA model, the LS (“adjusted”) means for each treatment arm and estimates of the difference (DI - PRN) will be given along with the respective two-sided, 95% CI together with two-sided p-values. In order to derive the final ANCOVA model, the following steps will be used:

[figure not shown]
1. The importance of the individual dependent variables on the primary outcome response variable will be testing using the primary ANCOVA model (see [Section 2.6.2](#) for details) for FAS (LOCF). Inclusion in the primary ANCOVA model when  $p < 0.2$ .
2. The backward stepwise regression procedure will be used to choose the optimal set of dependent variables from the set of statistically significant dependent variables tested in step 1. The significance level to stay in the ANCOVA model is  $p < 0.05$ .

Note: In case of inadequate results, further modification of the model may be required.

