1.2 Purpose

The purpose of this trial is to demonstrate that the change of best corrected visual acuity (BCVA) is comparable in patients treated with ranibizumab at the discretion of the investigator vs. treatment according to PRN scheme with monthly monitoring. Furthermore the number of injections and visits will be compared between treatment groups as well as morphologic parameters. Subgroups and new methods will enlarge our knowledge on the efficacy of ranibizumab. With the results of this study we aim to present a patient-tailored, investigator-based approach to monitor and treat patients with visual impairment secondary to Diabetic Macular Edema (DME).

2 Study objectives

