### 2.5.1 **Study treatment/ compliance**

#### 2.5.1.1 **Investigational treatment**

Descriptive statistics for the total number of ranibizumab injections will be presented for each treatment phase separately and overall by treatment group and total. Summary statistics for the number of injections per patient will be presented by frequency distribution (number of patients with 1 injection, number of patients with 2 injections, on up to the maximum number of injections for any one patient) for the given treatment phase and overall, and cumulatively.

Descriptive statistics will also be provided by treatment arm and total for:

- duration of the overall study period
- duration of the initial treatment phase
- duration of the maintenance phase
- duration of time between visits (overall and for maintenance phase)
- duration of time between injections (overall and for maintenance phase)

This table will also be repeated by actual treatment strategy. Furthermore, duration of time between visits and duration of time between injections will be presented overall and by actual treatment strategy from month 4 onwards

At each visit, the number and percentage of patients receiving or not receiving a ranibizumab injection will be summarized from baseline to month 11. Additionally, the reasons for no study treatment given will be summarized. This will include details for disease activity as recorded in the Ranibizumab dose administration eCRF (no disease activity, disease activity stable with maximum BCVA, BCVA and disease activity stable, Adverse event or disease activity present but patient refused additional study treatment). The denominator at each visit will be the number of patients for which a study treatment decision was recorded in the eCRF at that visit.

A frequency table will be presented at each visit showing the number and percentage of patients for overall and each individual stability compliance assessment category (see [Section 2.1.1](#) for definition of the stability compliance assessment) who stopped treatment due to one of the following three stability criteria:

- No disease activity (BCVA maximum, CRT minimum and no further signs of activity in morphologic parameters)
- Disease activity stable with maximum BCVA (no further improvement of other morphologic parameters)
- BCVA and disease activity stable (no further improvement of BCVA and other morphologic parameters).

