## 3 Sample size calculation

A sample size of 133 patients per treatment arm will have 90% power to establish non-inferiority at a margin of 4 letters for the 0.5 mg ranibizumab “at investigators discretion” dosing regimens in comparison to 0.5 mg ranibizumab PRN in the mean average change in BCVA based on a one-sided 0.025 significance level, assuming a treatment difference of 0 letters, a SD of 10 letters and an underlying normal distribution for an unstratified t-Test (nQuery Advisor 7.0).

The Phase III study (RESTORE) results in the FAS suggest a mean average change in BCVA of 6 letters with a SD of about 7-8 letters for ranibizumab. To account for some more variability related to the re-treatment concepts and subgroup treated with additional PRP laser in this study as compared to RESTORE, a SD of 10 letters is assumed. To account for some drop outs 150 patients will be randomized per treatment arm.

As outlined in the study protocol, section “Summary of protocol amendments” (study protocol version no.1 including Amendment 1); further recruitment of patients into this study was revised and reduced. New and relevant scientific evidence regarding treatment patterns with ranibizumab was published which did not justify continuing the trial with newly included

patients. Therefore recruitment was terminated at the time when 135 patients were enrolled into the study, resulting in a reduced sample size present for analysis.

As a consequence results are to be interpreted in a purely descriptive manner. With an estimate of about 120-150 patients to be enrolled by end of recruitment the expected power would be about 55-60% and will be evaluated accordingly.

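### Visit, injection and treatment-free-interval totals are not scaled to follow-up, so early leavers count as low-burden; the SAP's other time-based displays soften this but do not repair the endpoint

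*SAP*

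**What the plan says.** SAP 2.8.1 lists the number of visits, injections and TFIs among the secondary endpoints. Protocol 1.2 promises that "the number of injections and visits will be compared between treatment groups", and protocol 3.2 and 3.3 give fewer visits at comparable vision as the reason for the DI arm.

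The analysis is in two places:

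- **Visits and TFIs, SAP 2.8.2.** "Additionally, the total number of visits and total number of TFIs" to month 12 are summarised descriptively for the two arms. A note adds: "All data up to EoS will be used for FAS".
- **Injections, SAP 2.5.1.1.** "Descriptive statistics for the total number of ranibizumab injections will be presented for each treatment phase separately and overall", with frequency distributions, on the Safety Set.

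SAP 2.8.3 imputes nothing outside the LOCF endpoints, and protocol 5.5.9 does not replace withdrawn patients. No rate, offset, completer restriction or between-arm interval is given for these three counts. In the same SAP section, BCVA, CSRT and FCP thickness each get a DI-PRN difference with a 95% CI.

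**The concern.** A total count depends on how often the patient was seen or treated and on how long the patient was followed. A patient who leaves at month 4 contributes few visits and injections whatever the disease required. If more patients leave one arm than the other, that arm looks less burdensome with no difference in need. Three features of the plan add to this:

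- **Counting to EoS.** Patients who stop treatment but stay are asked to attend at least quarterly (protocol 5.5.9). Their later months add follow-up without study injections and possibly with sparse visits.
- **TFI definition.** Under SAP 2.1.1 a TFI ends at the next injection. An interval still open at exit therefore has no end and is not counted. This also applies to a patient who completes the study without needing another injection.
- **No precision.** Without an interval for the difference, the reader cannot judge how firm a contrast in burden is at this sample size.

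At stake is the reading of the result that motivates the DI regimen. No formal test is affected.

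**Working it through.** **1. The plan's own figures.** The documents give no number for this endpoint. The nearest is the sample size: "A sample size of 133 patients per treatment arm will have 90% power to establish non-inferiority", with margin 4, SD 10, true difference 0 and one-sided 0.025. The normal approximation gives 2 × (1.960 + 1.282)² × 10² / 4² = 131.3, so 132 per arm. The t-test gives 133 with power 0.901. The figure reproduces. It matters here only because randomising 150 to keep 133 implies an allowance of 1 − 133/150 = 11.3%. SAP 3 and protocol 9.7 state no rate, and the 150 belongs to the 300-patient plan.

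**2. Inputs for the illustration.**
- PRN schedule, protocol Table 6-1: 12 monthly post-baseline visits (visits 3 to 14).
- Injections, protocol 3.2, from the earlier phase III PRN trial: 7.0 over 12 months (a median, used here as a mean), of which 2.4 and 2.7 fell in the second half (midpoint 2.55).
- Assumed: the same true need and visit pattern in both arms, and leaving at month 6.

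**3. Loss per leaver and false difference.**
- Visits: 12 − 6 = 6 lost. A 10-point imbalance gives 0.10 × 6 = 0.60.
- Injections: 2.4 to 2.7 lost. A 10-point imbalance gives 0.24 to 0.27; at the midpoint, 0.10 × 2.55 = 0.26.

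**4. Range for a 10-point imbalance.** The first-half injections (7.0 − 2.55 = 4.45) and second-half injections (2.55) are each spread evenly.

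| Leaving time | Visits lost per leaver | Injections lost per leaver | False difference, visits | False difference, injections |
|---|---|---|---|---|
| Month 3 | 9 | 4.8 | 0.90 | 0.48 |
| Month 6 | 6 | 2.55 | 0.60 | 0.26 |
| Month 9 | 3 | 1.3 | 0.30 | 0.13 |
| Uniform over the year | 6.5 | 3.0 | 0.65 | 0.30 |

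A 20-point imbalance (5% vs 25%, uniform) gives 1.3 visits and 0.6 injections.

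**5. Equal leaving.** With 11.3% leaving each arm at mid-year, each mean falls by 0.113 × 6 = 0.68 visits and 0.113 × 2.55 = 0.29 injections. With equal need the difference stays zero. A true second-half difference shrinks by the leaving share, about 11%.

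**6. Does a rate help?** Take 5% vs 15% leaving at mid-year.
- Patient-months per patient: 0.95 × 12 + 0.05 × 6 = 11.7, and 0.85 × 12 + 0.15 × 6 = 11.1.
- Post-baseline visits: 12 − 0.05 × 6 = 11.7, and 12 − 0.15 × 6 = 11.1. Both are 12.0 per 12 patient-months, so the false difference disappears.
- Injections: (7 − 0.05 × 2.55) × 12/11.7 = 7.05, and (7 − 0.15 × 2.55) × 12/11.1 = 7.15. The false difference falls from 0.26 to about 0.1, in the opposite direction, because injections are front-loaded. With uniform leaving the rates are 7.02 and 7.08, a gap of about 0.05.

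**7. What the companion displays cover.**
- Time between visits and between injections (SAP 2.5.1.1): an interval needs a later visit or injection to close it, so time after the last one is lost.
- Percentage injected at each visit (2.5.1.1): the denominator is patients with a recorded treatment decision at that visit.
- Kaplan-Meier (2.5.1.1.2): first re-treatment only.
- Observation period (2.5.1.1): summarised separately, never combined with the counts.

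**The case against.** The strongest reply is that the SAP already shows burden on a time scale. Time between visits and between injections is given by arm, overall and for maintenance. Mean time between visits is close to the inverse of a visit rate, and a month-4 leaver does not look low-burden on it. Disposition, attendance by visit and the length of observation are also tabulated by arm, so unequal leaving would be visible. This stands as mitigation. A reader might infer that the plan ignores time on study altogether; these displays show that it does not. They still leave the named endpoint as a raw total.

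Two further inferences are tempting and fail. One is that the plan assumes 11% dropout: that figure is only back-calculated from 133 and 150. The other is that a mid-year leaver loses half of 7 injections, giving 7 × 0.5 × 0.10 = 0.35. The second-half counts in protocol 3.2 contradict an even spread and give about 0.26.

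Scale also counts. Protocol 3.2 reports 20.5 visits under PRN against 12.5 to 12.8 under treat-and-extend over 24 months, a gap of 7.7 to 8.0, or about 4 a year if even. If DI saved as much (an assumption), 0.6 visits is about 15% of that and would not reverse the reading. The same trial's injection medians, 12 against 10 over 24 months, differ by only about 1 a year, so 0.26 matters relatively more for injections.

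Finally, protocol 5.5.9 encourages patients who stop treatment to stay to month 12, which limits lost follow-up. The analyses are declared purely exploratory, and side-by-side tables arguably meet the promise to compare. Both points lower the weight of the issue but do not remove it.

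**Conclusion.** The point holds in limited form. Visits, injections and TFIs are reported as raw totals that fall with early exit, and no other display repairs that. Assuming a 10-point imbalance at mid-year and no true difference, the false contrast is about 0.6 visits and 0.26 injections. Across leaving times from month 3 to month 9 the range is 0.3 to 0.9 visits and 0.13 to 0.48 injections. These sizes rest on an assumed imbalance, the monthly PRN visit pattern in both arms and injection counts from an earlier trial. The documents give no dropout by arm. With equal leaving, both arms are understated and the contrast is largely kept. The documents do not support saying that the burden comparison is invalid, or that it is tilted towards DI: the direction depends on which arm loses more patients. This is a minor, inexpensive improvement to a descriptive result.

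**What to change.** Keep the raw totals and add the following beside them:

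1. Post-baseline visits per patient-year of observation, to EoS.
2. Injections per patient-year on treatment, to EoT, or to EoS if treatment was not stopped early. Do not use the study treatment period of SAP 2.5.1.1 as the denominator: it ends at the last administration and so drops the treatment-free time after it. Time to the last visit is also unsuitable for patients who stopped treatment but stayed.
3. Both rates overall and, descriptively, for the maintenance phase.
4. The DI-PRN rate difference or ratio with a 95% CI, from a Poisson model with log-time offset and robust variance, or from a bootstrap. A negative binomial model is a poor choice: PRN visits are nearly fixed at one a month, and that model cannot go below Poisson variance (SD about √12 = 3.5 at a mean of 12).
5. A completer summary of the counts, as a check on the front-loading of injections.
6. TFIs still open at exit reported as censored rather than omitted.

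The cost is one small model per count and a few table lines, with no new data; observation time is already derived. The downsides are a little more exploratory output and a slight overcorrection for front-loaded injections (about 0.05 to 0.1 injections in the illustration), which items 3 and 5 help the reader to judge.

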As a consequence in this study we want to test an alternative treatment scheme, where the investigator decides when to monitor and/or treat the DME patient.

In addition this study might provide data on predictors by evaluating which patient needs more frequent monitoring and which patients need less monitoring. To further broaden the knowledge on DME and DR and to better reflect the daily routine in the clinics, patients with additional proliferative diabetic retinopathy (PDR) and retinal ischemia will not be excluded.

This study will also investigate new functional parameters (e.g. microperimetry) optionally at equipped centers.

Meanwhile the label of ranibizumab has been updated with corresponding data and is now supporting individualized treatment and monitoring intervals for patients with DME (see chapter “Summary of Amendment 01”).

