5.1.2 Additional study treatment

Focal/grid laser can be applied additionally in both arms but earliest at month 3.

Patients with indication for PRP (e.g. PDR, large non-perfusion areas, severe non-proliferative diabetic retinopathy) will be treated with additional panretinal photocoagulation (PRP) at baseline or at least within 3 months after randomization in both arms.

Macular ischemia should not be treated with PRP according to already mentioned guidelines.

For more details please refer to chapter [5.5.3.2 Handling of other study treatment](#).

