5.5.3.2.2 Panretinal photocoagulation (PRP)

Patients with indication for panretinal photocoagulation (PRP) (e.g. PDR, large non-perfusion areas, severe non-proliferative diabetic retinopathy) will be treated additional with PRP at baseline or at least within 3 months after randomization in both arms.

PRP should be applied according common laser recommendations listed in Appendix 2: PRP (panretinal laser photocoagulation) procedures.

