9.5 Analysis of secondary and other variables

9.5.1 Efficacy variables

The analysis of the secondary efficacy objectives will focus on the study eye only and it will be based on the FAS.

At all the time points assessed, each efficacy variable will be presented graphically (where appropriate) and descriptive statistics provided based on absolute values and changes from baseline.

Of note is that for patients randomized to the DI, no monthly visit and consequently no monthly reporting schedule exists. Therefore efficacy data collected by visit will be described on a bi-weekly schedule for the DI arm. Furthermore and in order to allow for a visualization of data of both arms on a monthly basis, data collected in between two monthly visits (e.g. at Month 5.5) will be reported at the following monthly visit.

For continuous and ordered categorical variables, changes from baseline will be compared between treatment groups using ANCOVA models (with the baseline covariate)/ T-test. For treatment differences, 95% confidence intervals will be calculated for differences of means (based on ANCOVA models).

Secondary Efficacy variables

The variables related to the secondary objectives are described below:

1. Mean change from baseline in BCVA from baseline to month 12.
2. Number visits and injections, and treatment free intervals
3. Changes in central subfield retinal thickness (CSRT) and foveal center point thickness by SD-OCT.
4. Comparison of changes of 1,2 or more steps in DRS retinopathy scale between treatment arms compared to baseline
5. ANCOVA analysis of primary outcome with the additional covariates “relevant changes of HbA1c, blood pressure, lipid level”

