## 2.8.1 Secondary endpoints

The following secondary efficacy endpoints will be evaluated:

- Change of BCVA in ETDRS letters from baseline to month 12
- Number of visits, injections and TFIs
- Change of CSRT ( $\mu\text{m}$ ) from baseline to month 12
- Change in FCP thickness ( $\mu\text{m}$ ) from baseline to month 12
- Change in 0, 1, 2 or more steps in DRS from baseline to month 12
- ANCOVA analysis of primary outcome with the additional covariates: relevant changes of HbA1c, blood pressure (systolic, diastolic), and lipid levels (cholesterol, HDL-cholesterol, LDL-cholesterol, triglycerides)

Changes in CSRT and FCP thickness will be evaluated by the CRC assessing OCT images. Changes in DRS will be evaluated by the CRC scoring CF Photography and FA images and will be defined in 5 severity levels:

1. Mild non-proliferative retinopathy (NPDR)
2. Moderate NPDR
3. Severe NPDR
4. Proliferative DR
5. Status post panretinal laser coagulation - not gradable

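### The retinopathy step-change percentages leave out eyes graded 5 after on-study panretinal laser, and no rule counts progression leading to that laser as worsening

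*SAP*

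**What the plan says.** - **Scale.** SAP 2.8.1 defines the endpoint as change in DRS steps from baseline to month 12, graded by the central reading center on five levels: mild, moderate and severe non-proliferative disease (1 to 3), proliferative disease (4), and a fifth, "Status post panretinal laser coagulation - not gradable".
- **Derivation.** SAP 2.8.2 reports the number and percentage of patients per arm in each improvement or loss category on the FAS with LOCF. It then restricts the step change: "This improvement/ loss will only be derived for those patients with a DRS score of 1, 2, 3, or 4", at both baseline and month 12. The percentage denominator is not stated. The next sentence adds a baseline-to-month-12 shift table of DRS score, with no stated restriction to levels 1-4.
- **Laser.** Protocol 5.5.3.2.2 gives the PRP indications by example, with the timing: "e.g. PDR, large non-perfusion areas, severe non-proliferative diabetic retinopathy) will be treated additional with PRP at baseline or at least within 3 months". The three months run from randomization and the rule covers both arms; 5.1.2 says the same. Eyes of this kind are enrolled: in Protocol 1.1, "patients with additional proliferative diabetic retinopathy (PDR) and retinal ischemia will not be excluded".
- **Protocol endpoint.** Protocol 9.5.1 asks for "Comparison of changes of 1,2 or more steps in DRS retinopathy scale between treatment arms compared to baseline", with no restriction to levels 1-4. SAP section 4 declares no change from the protocol.
- **Related outputs.** SAP 2.5.1.2 tabulates laser by type and the reason for laser by visit. SAP 2.2.1 plans a PRP subgroup that includes change in proliferative disease. SAP 2.1 provides a missing row for categorical tables.
- **Status.** SAP 2.8.2 treats the secondary analyses as purely descriptive and specifies no test for DRS.

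**The concern.** Whether an eye enters the step-change table depends on an event after randomization, PRP, that is tied to the outcome being measured. An eye that worsens and is not lasered counts as a loss. An eye that worsens by the same amount, is lasered and is graded 5 does not count at all. Under Protocol 3.2 the treating physicians are not masked, so the use of laser could also differ between arms.

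At stake is whether a reader can take the loss percentages, and the DI-PRN contrast in them, at face value. The restriction is also a narrowing of the protocol endpoint that the SAP does not declare.

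**Working it through.** **1. Plan's own figure.** There is none to reproduce. The documents give no expected DRS distribution, PRP rate or worsening rate. The stated sample size concerns the BCVA endpoint only.

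**2. Tracing eyes through the rules.**

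| Baseline level | On study | Month 12 level | Step-change table |
|---|---|---|---|
| 2 | Progresses, no PRP | 4 | Loss of 2 steps |
| 2 | Progresses, PRP | 5 | No step change |
| 4 | PRP for baseline indication | 5 | No step change |
| 5 | Any | Any | No step change |

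The first two rows can be the same disease course; only the laser differs. LOCF does not clearly restore the second row. SAP 2.6.3 replaces missing values, and level 5 is an observed grade. Fundus photographs are required only at screening, end of treatment and end of study (Protocol 6.4.3), so there is little to carry forward.

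**3. Size within one arm (illustration, assumed inputs).** Let there be 65 eyes per arm (Protocol synopsis), all at level 1-4 at baseline. Let b be the share lasered for a baseline indication and graded 5, w the true worsening rate in the other eyes, and L the share of worsening eyes lasered and graded 5 by month 12. Assumed ranges: b 0-30%, w 5-20%, L 25-75%. If the denominator is the eyes with a derived step,

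reported loss = w(1 - L) / (1 - wL).

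The factor (1 - b) cancels, and so does the 65. For w = 10% and L = 50%: 0.05 / 0.95 = 5.3%.

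| True w | L = 25% | L = 50% | L = 75% |
|---|---|---|---|
| 5% | 3.8% | 2.6% | 1.3% |
| 10% | 7.7% | 5.3% | 2.7% |
| 20% | 15.8% | 11.1% | 5.9% |

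**4. Between arms, from the same table.**
- Same laser use (L = 50%), true 20% against 10%: reported 11.1% against 5.3%. The 10-point gap shrinks to 5.8.
- Same true rate (10%), L = 25% against 75%: reported 7.7% against 2.7%, a gap of 5.0 points where none exists.
- True 20% with L = 25% against true 10% with L = 75%: 15.8% against 2.7%. The gap grows to 13.1 points.
- True 20% with L = 75% against true 10% with L = 25%: 5.9% against 7.7%. The order reverses.

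**5. Role of the denominator.** Take b = 20%, w = 10%, L = 50%, in expected counts.
- Lasered for baseline disease: 0.20 × 65 = 13.
- Others: 52, of whom 5.2 worsen and 2.6 of those are lasered.
- No step change: 13 + 2.6 = 15.6 of 65 (24%).
- Derived-eye denominator: 2.6 / 49.4 = 5.3%.
- All 65 as denominator, same numerator: 2.6 / 65 = 4.0%.
- All 65, lasered progressors counted as worsened: 5.2 / 65 = 8.0%.

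A fuller denominator alone does not bring the progressors back; they need their own row and a sensitivity count. The denominator also has its own effect. With L = 0, the derived-eye figure is 5.2 / 52 = 10.0% against 5.2 / 65 = 8.0% over all eyes, so removing eyes lasered for baseline disease raises the loss percentage.

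**The case against.** Level 5 is not gradable, so declining to compute ordinal steps from it is defensible. The endpoint is secondary and descriptive. Counting PRP as worsening would replace a masked reading-center grade with an unmasked physician's decision, and PRP has indications, such as large non-perfusion areas, that are not themselves a DRS step. All of this stands. It is why the remedy is a labelled row and a sensitivity summary, not a new main definition.

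Three stronger readings are tempting, and the documents do not support them:

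- **Progression leading to laser is lost from the results altogether.** The shift table is not limited to levels 1-4, the laser tables give type and reason, and there is a PRP subgroup. Eyes with no derived step may also fall in the missing row of SAP 2.1, though the SAP does not say so, and there they would be pooled with absent images. The gap is in the step percentages. A shift to level 5 does not separate laser for baseline disease from laser for progression.
- **The comparison leans towards no difference.** This follows only if worsening eyes are lasered about equally often in both arms. Step 4 shows that the gap can also grow, arise from nothing or reverse. Much early PRP will reflect disease present before randomization, which should balance across arms on average.
- **The rows for improvement of 2 or more steps are nearly empty by construction.** From level 2 the largest gain is 1 step, but the SAP admits levels 3 and 4 at baseline. The claim needs every such eye to be lasered and then graded 5. PRP is conditional on an indication, and the reading center records signs of panretinal laser separately from the DRS grade (SAP 2.4.3), so the two need not coincide.

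**Conclusion.** The point holds for the step-change percentages. They exclude every eye at level 5 at either time, and no planned rule counts progression that leads to PRP as worsening. The percentages can therefore understate worsening, and the DI-PRN comparison can be distorted in either direction depending on laser use in each arm. Under the assumed ranges, true worsening of 10% would be reported as 2.7% to 7.7%. These figures only illustrate the mechanism; the real size is unknown, and it could be small if PRP for on-study progression is rare. The primary BCVA analysis is unaffected. The 1-4 restriction should be declared, since Protocol 9.5.1 has none. This is an inexpensive improvement to a stated secondary endpoint.

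**What to change.** - In SAP 2.8.2, use all FAS patients in each arm as the denominator for the step-change percentages.
- Show level 5 in its own rows, separate from missing images: level 5 at baseline; PRP for an indication present at baseline; PRP for on-study progression. Keep level 5 as a category in the shift table.
- Add one descriptive sensitivity summary that counts PRP for on-study progression, in eyes graded 1-3 at baseline, as worsening. Level 4 eyes cannot lose a step on this scale.
- List the 1-4 restriction in SAP section 4 as a change from Protocol 9.5.1.

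The cost is a few table rows and one extra summary. Laser applications are already recorded (Protocol 5.5.3.2), and the reason for laser is taken from the eCRF (SAP 2.5.1.2). The documents do not list the reason categories. If these do not separate baseline indication from progression, the split has to lean on laser dates and will be approximate, so the rule should be written down before unmasking. The remaining weakness is that PRP is an unmasked decision and an imperfect marker of progression, so this should stay a sensitivity summary.
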